1.3.2.2 Preclinical toxicities

“JNJ-40346527 was evaluated at 10 mg/kg in rats after 3 months of dosing and 25 mg/kg in dogs after 9 months of dosing. In general, pathology findings were mild and reversible after the 1 month recovery period. Relevant toxicities observed with JNJ-40346527 across the species that are considered potentially related to the mode-of-action of CSF-1R inhibition are summarized in **Table 1**”^a.

Table 1. Summary of preclinical toxicities associated with CSF-1R inhibition^a

Hematopoietic system:	
• Bone marrow hypocellularity with decreased erythropoiesis and increased accumulation of adipose tissue;• Peripheral blood changes with decreased lymphocytes and increased neutrophil counts
Kidney:	
• Nephropathy and increased glomerular thickness;• Urinary calcium decrease
Liver:	
• Transaminase (AST and ALT) elevations
Blood vessels:	
• Fibrinoid necrosis
Connective tissue:	
• Mucinous accumulation
Bone:	
• Increased thickness of the epiphyseal plate in the femur
Spleen:	
• Accumulation of congestion and pigment laden macrophages
Testicles:	
• Bilateral degeneration
Skin:	
• Sensitizing potential
Eyes:	
• Severe irritant

1.3.3 CLINICAL STUDIES OF JNJ-40346527

“Clinical information on the PK/PD, safety, and efficacy of JNJ-40346527 are available for 178 participants that enrolled into 3 completed clinical studies conducted in distinct populations:

- Phase 1 Study 40346527EDI1001 in healthy volunteers (n = 94)
- Phase 2a Study 40346527ARA2001 in subjects with active rheumatoid arthritis (n = 63)
- Phase 1/2 Study 40346527HKL1001 in subjects with Hodgkin’s lymphoma (n = 21)”^a

1.3.3.1 Pharmacokinetics in Humans

“The pharmacokinetic characteristics of JNJ-40346527 were assessed in all 3 clinical studies conducted so far. Across studies the following main PK characteristics of JNJ-40346527 following multiple daily oral regimen were observed:

- Rapid absorption following oral administration
- Dose proportional increase of C_{max} (following QD dosing) and AUC (QD and BID dosing)
- Mean terminal half-life (t_½) of ~140 hours
- Dose-related systemic accumulation
- Steady state level reached by ~21 days of dosing
- No apparent sex related differences in PK characteristics
- No impact of food on PK characteristics”^a

1.3.3.2 Metabolism in Humans

“The major JNJ-40346527 metabolite in humans, M7, is generated by mono oxygenation. The formation of M7 is due largely to the CYP2C subfamily, specifically CYP2C8, and CYP2C19. M7 was found to be slightly (<2-fold) more potent than JNJ-40346527 in an in vitro CSF-1R kinase assay. The formation of the other metabolite M2 is largely due to CYP3A4. Radiolabeled studies have not been conducted in humans, however in animals ¹⁴C-JNJ-40346527 was highly bound (≥99%) to plasma proteins in all species tested. After 25 mg/kg oral administration of ¹⁴C-JNJ-40346527 to male rats and male dogs, radioactivity was excreted primarily in feces.”^a

1.3.3.3 Drug Interactions

JNJ-40346527 is a reversible inhibitor of primarily CYP3A4 and CYP2C8 and to a lesser extent of several other CYP isoforms (i.e., CYPs 2B6, 2C9, 2C19, and 2D6) in vitro. JNJ-40346527 increased the plasma exposure of midazolam (by ~65%) in a clinical Phase 1 study, suggesting a weak inhibition of CYP3A4 at clinically relevant doses.

1.3.3.4 Safety in Humans

JNJ-40346527 was generally well tolerated by (i) healthy volunteers, (ii) subjects with active RA, and (iii) subjects with relapsed or refractory HL. The most frequent JNJ-40346527 treatment-emergent adverse events (AEs) are shown in **Table 2.**^a

Table 2. Summary of JNJ-40346527 treatment emergent adverse events^a

Organ system	Treatment emergent AEs
Gastrointestinal:	
• diarrhea,• nausea,• vomiting• constipation,• abdominal pain,• gastroesophageal reflux
Hematologic:	
• anemia,• decrease in WBC (neutrophils, monocytes, lymphocytes),• reticulocytes
Hepatic:	
• AST and ALT increase
Pulmonary:	
• dyspnea
Constitutional symptoms:	
• pyrexia,• headache,• back pain
Laboratory changes:	
• increase in creatinine kinase and lactate dehydrogenase

1.3.3.5 Efficacy in Humans

“The preliminary efficacy of JNJ-40346527 was evaluated in participants with active rheumatoid arthritis in Study 40346527ARA2001. No consistent evidence of efficacy was observed in subjects with RA receiving JNJ-40346527 compared with subjects receiving the placebo.

In study 40346527HKL1001, limited efficacy was observed for JNJ-40346527 evaluated in participants with relapsed or refractory Hodgkin’s lymphoma. One out of 20 evaluable subjects (5.0%) demonstrated complete response. An additional 11 subjects (55.0%) experienced stable disease, while 8 subjects (40.0%) had progressive disease.”^a

1.3.4 SMALL MOLECULAR KINASE INHIBITOR SCREEN

The kinase inhibitor screen is an *ex vivo* drug screening platform that facilitates functional evaluation of small molecule inhibitors on primary patient samples.¹⁵ In this assay, a library of small-molecule inhibitors is plated in 384-well format in 7-point concentration series. Primary AML patient specimens are cultured on the assay plates (10,000 cells/well) for 3 days, after which drug sensitivity is assessed by a tetrazolium-based viability assay. A probit dose-response curve is generated for each drug, and IC₅₀ values are computed based on the probit models. Effective selection of drugs for patients using this assay has been achieved in numerous n-of-1 studies and within the context of ongoing phase 1b ([NCT02779283](#)) and phase 2 ([NCT01620216](#)) trials for newly diagnosed and relapsed/refractory AML, respectively.

1.4 RATIONALE

CSF-1R inhibitors have caused growth inhibition in 20-25% of AML samples screened with the *ex vivo* assay (in revision). In particular, treatment with the CSF-1R inhibitor JNJ-28312141 has resulted in a sensitivity rate of ~37% (as defined by a sensitivity cutoff of ≤ 40 nM). Response to CSF-1R inhibition does not correlate with intrinsic CSF-1R expression in leukemia cells, but rather appears to be related to CSF-1R expression in a subpopulation of supportive cells that provides paracrine growth signals. Our underlying hypothesis is that JNJ-40346527 targets a subpopulation of supportive cells, which leads to interruption of paracrine survival signals to leukemia cells, and subsequent leukemia cell death. This is similar to the mechanism of action of JNJ-40346527 in tenosynovial giant cell tumor; however, in tenosynovial giant-cell tumors the malignant cell secretes CSF-1, which recruits non-malignant CSF-1R+ monocytes and histiocytes. In our model, the non-malignant CSF-1R+ population is supporting malignant leukemia cell survival by an unknown paracrine signal and this signal is turned off after CSF-1R inhibition.

We hypothesize that the CSF-1R inhibitor JNJ-40346527 will be effective in treating a subset of AML patients, and that given the absence of genetic or other markers, we can select sensitive patients using our *ex vivo* functional screen.

1.4.1 DOSE RATIONALE

Results of study 40346527HKL1001, investigating JNJ-40346527 in patients with relapsed or refractory Hodgkin's lymphoma found optimal inhibition of phosphorylated CSF-1R at 150 mg twice a day.¹⁶ In this study, participants will receive JNJ-40346527 at 150 mg PO twice daily in continuous 28-day cycles.

1.5 POTENTIAL RISKS AND BENEFITS

1.5.1 KNOWN POTENTIAL RISKS

Available clinical safety data suggest that JNJ-40346527 is likely to be safe and well tolerated. Based on the mechanism of CSF-1R inhibition, however, there is a risk that JNJ-40346527 may induce side effects when administered as single agent (or in combination with other agents) that have not been observed yet and that may be of severe intensity. Toxicities reported with other CSF-1R targeting small molecules or antibodies that have not yet been reported with JNJ-40346527 include:

1. *FPA008*, a small-molecule CSF-1R inhibitor. Phase 1 study data collected following participant exposure to FPA008 was associated with AEs of eyelid edema, facial swelling,

pruritus, and blurred vision.¹⁷

2. *PLX3397*, a small-molecule CSF-1R inhibitor. In a Phase 2 study conducted with the *PLX3397*, cases of hair depigmentation and liver toxicity were observed.¹⁸
3. *Emactuzumab*, a CSF-1R inhibiting antibody. Investigators of a Phase 1 study noted that *Emactuzumab* was associated with cases of lupus erythematosus and cases of cutaneous toxicities, including; erythema, pruritus, dermatitis and facial edema were reported.¹⁹

1.5.2 KNOWN POTENTIAL BENEFITS

[figure not shown]
Given the lack of treatment options for treating relapse or refractory AML, the current study may provide access to a new treatment approach not previously available. It cannot, however, be guaranteed that participants in this study will directly benefit from treatment during participation, as the clinical trial is designed to provide information about the safety and effectiveness of the investigational approach.

1.6 CORRELATIVE STUDIES BACKGROUND

The goals of the correlative studies are twofold:

1. Identify the biomarkers that correlate with clinical response, and
2. Identify the effect of JNJ-40346527 on leukemia cells and the immune microenvironment and potential drug combinations for future trials.

The information from the second goal will be important to understand what cells are targeted by CSF-1R inhibition, and identify additional targets for combination trials. For example, removing supportive paracrine CD14⁺ cells from the leukemia microenvironment may uncover novel kinase inhibitor sensitivities in the leukemia cells that were masked by paracrine survival signals (**Figure 4**). Alternatively, CSF-1R inhibition may enhance expression of immune checkpoint proteins such as PD1 or PDL1 in the leukemia microenvironment, facilitating use of immune checkpoint inhibitors in AML.

Specific cell populations in the leukemia immune microenvironment will also likely be modulated by JNJ-40346527, such as T-cell and NK cell populations, which could potentially enhance antibody-dependent cellular cytotoxicity of targeted antibodies such as talacotuzumab (CSL362/JNJ-56022473). Understanding which patients are most likely to respond to JNJ-40346527 treatment, and how the leukemia cells and their immune microenvironment are affected by treatment, will be critical to develop effective combinations in the future.

2. OBJECTIVES

2.1 PRIMARY OBJECTIVES

Evaluate preliminary efficacy of JNJ-40346527 in participants with relapsed/refractory AML, assessed by best objective response rate (>PR).

2.2 SECONDARY OBJECTIVES

1. Assess the safety of JNJ-40346527 in participants with relapsed or refractory AML.
2. Assess the duration of disease response associated with JNJ-40346527.
3. Overall incidence of treatment-related and non-treatment related toxicity.
4. Duration of response.
5. 12-month event-free survival.
6. 12-month overall survival.

2.3 EXPLORATORY OBJECTIVES

[figure not shown]
1. Evaluate the pharmacokinetics of JNJ-40346527 and effective inhibition of CSF-1R in marrow aspirates using plasma inhibitory assays, with established CSF-1R-sensitive cell lines.
2. Identify the effect of JNJ-40346527 on leukemia cells and the immune microenvironment.
3. Identify and quantify the specific subpopulation of cells that express CSF-1R in participants and correlate these with clinical response to JNJ-40346527.
4. Analyze the frequency of mutations using genomic DNA from leukemia participants to determine if there is a genetic signature that predicts response to JNJ-40346527.
5. Using RNA sequencing (RNAseq), identify an expression signature in CSF-1R⁺ cells that predicts patient response.
6. Evaluate the effect of JNJ-40346527 on immune cell populations (cytotoxic T cells, etc.) and phospho-signaling proteins by CyTOF analysis in pre- and post-treatment samples in order to identify biomarkers that predict patient response and prioritize potential combination strategies for future clinical trials.
7. Determine how leukemia cells change in response to CSF-1R inhibition by assessing cells collected pre- and post-treatment using an *ex vivo* sensitivity to a panel of small molecule inhibitors to determine what new drug sensitivities may emerge in AML cells after CSF-1R inhibition.

3. STUDY DESIGN AND ENDPOINTS

3.1 DESCRIPTION OF THE STUDY DESIGN

Refer to Section 10, **STATISTICAL CONSIDERATIONS** for additional information regarding statistical methods used in this study.

This is a Phase 2, Simon 2-stage minimax design to determine clinical efficacy of JNJ-40346527 in relapsed/refractory AML. Participants must meet the inclusion criteria, have none of the exclusion criteria, and have provided written informed consent before the conduct of any screening tests not performed routinely in their treatment.

Results from preclinical studies suggest that responsive patients may be selected by using an *ex vivo* assay with JNJ-40346527. Eligible participants will be divided into two treatment arms based on an *ex vivo* sensitivity of AML cells derived from either bone marrow aspirates or peripheral blood (if inaspirable and $\geq 20\%$ circulating blasts). Participants with an *ex vivo* IC_{50} that is $\leq 20\%$ of the median IC_{50} (to be determined with preclinical testing) will be considered sensitive to JNJ-40346527 (termed “assay positive”), whereas those with an $IC_{50} > 20\%$ of the median IC_{50} will be considered insensitive (termed “assay negative”) for purposes of assignment. This threshold is set prior to the study start and does not change. This will result in 2 study arms: 1) Assay positive and 2) Assay negative (Figure 6). Patients that screen fail (for example indeterminate assay results or insufficient sample) will not be included in the study. Patients can rescreen per provider discretion.

For each arm, 7 participants will be enrolled in the first stage. If there is at least 1 response among the first 7 participants, the study will proceed to the second stage, in which an additional 7 participants will be enrolled. The treatment is considered promising if there are at least 3 responses among 14 participants. The best objective response and exact confidence intervals will be estimated using the binomial distribution for each arm.

We anticipate that *ex vivo* sensitivity will predict participants’ response and that only the assay positive arm will continue to enroll in stage 2. The expected total enrollment of both Arms would be 21 participants in this case. If no participant responds in either treatment arm, the enrollment will end with 14 patients. If ≥ 1 out of 7 eligible participants respond to JNJ-40346527 in both the assay positive and assay negative arms, then both arms will continue to stage 2. In this case, the maximum enrollment would be 28 participants.

This study has a stopping rule for both futility (a lack of efficacy) and safety. No response among the first 7 patients is defined as futility and will halt each either arm of the study.

Likewise, excess toxicity will suspend enrollment if the lower 90% confidence interval for Grade 3 or higher treatment-related toxicity exceeds 30% (considered acceptable dose-limiting toxicity (DLT) incidence).

3.2 STUDY ENDPOINTS

3.2.1 PRIMARY ENDPOINT

Endpoint	Start	End
1. Best objective response rate.	First dose of JNJ-40346527	Over 3 cycles

3.2.2 SECONDARY ENDPOINT(S)

Endpoint	Start	End
1. Overall incidence of treatment-related and non-treatment related toxicity..		30 days after last dose of study agent
2. Duration of response. For patients that achieve \geq PR, how long do they maintain this response before progression.	First dose of JNJ-40346527	
3. Event-free survival at 12-months		12 months from first dose
4. Overall survival at 12-months		Death (or date of last contact)

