6.3 TREATMENT PERIOD AND MAINTENANCE

Participants will receive JNJ-40346527 at 150 mg PO twice daily in continuous 28-day cycles. Initial response will be assessed by bone marrow biopsy after cycles 1-3 and then every 3 months thereafter. Further study assessments will be performed as outlined in the Section 7.10, Schedule of Events .

Treatment with JNJ-40346527 will continue until disease progression or stopping rules are triggered as a result of either excess toxicity or lack of efficacy (refer to Section 10.2.4).

Disease progression will be defined as any patient with response \geq PR who then loses PR based upon the original pre-treatment marrow sample (PR defined as \geq 50% decrease in marrow blasts to 5-25% of marrow). For example, a patient with 30% blasts on pre-treatment

marrow who achieved CR with 4% blasts and then was found to have 6% blasts with continued hematologic recovery on subsequent marrow (PR) would remain on trial until subsequent marrow blasts were >15%, or with loss of hematologic response. Patients with stable disease who continue to receive clinical benefit per PI review may remain on study drug.

If a participant achieves a complete remission (CR) and is deemed a candidate for allogeneic stem-cell transplant, JNJ-40346527 should be discontinued 7 days before initiation of the conditioning regimen. Treatment with JNJ-40346527 may be resumed 30-100 days after the transplant if patients has a relapse of their disease, no active GVHD, and after review by the PI.

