7.2.5 BONE MARROW EXAM

Bone marrow aspirate must be collected at the visits outlined in the Section 7.10, Schedule of Events (Cycle 1 Day 29, Cycle 2 Day 29, Cycle 3 Day 29, and every 3 months following Cycle 3 Day 29. Additional bone marrow evaluations may occur if clinically indicated at the discretion of

the investigator (e.g., at the time of suspected disease progression or disease remission.)

Bone Marrow Aspirate will be collected to assess:

- Hematopathology review
- myeloid:erythroid ratio per standard of care
- Cellularity (%)
- blast quantification per standard of care.
- Cytogenetics will be performed as standard of care.
- Pharmacokinetic assay described in Section 7.3.1. (5-8ml in sodium heparin)
- Flow cytometry: as standard of care per institutional standards and exploratory analysis described in Section 7.3.2.

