7.10 SCHEDULE OF EVENTS

Ex vivo screening	X		X	X		X			
FACS	X			X		X			
RNAseq	X	X		X		X			
Research Blood Samples ^K	X	X	X	X	X	X	X	X	

* In general, assessments/procedures are to be performed on Day 1 and prior to the first dose of treatment for each cycle unless otherwise specified. Treatment cycles are 28 days; however the treatment cycle interval may be increased due to toxicity according to the dose modification guidelines provided in Section 6.2.. If the interval is increased, all procedures except imaging should be performed based on the new dosing schedule.

** In general, the window for each visit is \pm 7 days unless otherwise noted.

*** Point of care CBC will be run every 2 weeks during Cycle 2. Once a cycle in subsequent cycles (Cycle 3+).

† Study treatment will end upon evidence of disease progression as defined by IWG for AML. Refer to Section 8 for additional details.

‡ Participants will be followed until death. Participants may be contacted by phone, and survival status will be collected and documented

^ JNJ-40346527 (150 mg) is administered PO twice daily.

B For concomitant medications – enter new medications started during the trial through the EOT visit. Record all medications taken for grade 3 and 4 SAEs as defined in Section 9.6.

C Full physical exam at screening visit. Direct physical exam for all other visits. All physical exams will include assessing weight, vital signs, and ECOG performance status. Height will be measured at screening visit only.

D Chest X-ray at screening will be performed within 28 days prior to the first dose of trial treatment. Scans performed as part of routine clinical management are acceptable for use as the screening image if they are of diagnostic quality and performed within 28 days prior to the first dose of trial treatment.

E After Cycle 1, pre-dose lab samples can be collected up to 72 hours prior to the scheduled time point. Hematology and biochemistry tests should be collected pre-dose on Day 1 of every 28 day cycle. Testing for HCV B or C will only take place during screening.

F For women of reproductive potential, a urine pregnancy test should be performed within 14 days prior to first dose of trial treatment. If urine pregnancy results cannot be confirmed as negative, a serum pregnancy test performed by the local study site laboratory will be required. Pregnancy tests (serum and/or urine tests) should be repeated, if required, per institutional guidelines.

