G Peripheral blood may be used in place of bone marrow and blast cells comprise \geq 20% of circulating nucleated cells.

H Standard of care bone marrow exams are done at screening and Day 29 for Cycles 1-3, and every 3 months for subsequent cycles.

I Skin punch biopsy will be collected once anytime during the study.

J AEs and laboratory safety measurements will be graded per NCI CTCAE version 5.0. All AEs, whether gradable by CTCAE or not, will also be evaluated for seriousness. Record grade 3 and 4 AEs occurring within 30 days after the last dose of trial treatment. Report grade 3 and 4 hem and non-hem SAEs (related and unrelated to trial treatment) occurring up until 90 days after the last dose of trial treatment, or the start of new anti-cancer treatment, whichever comes first. Afterwards, report only SAEs that are related to trial treatment.

K Research blood samples will be drawn during standard of care lab draw.

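### Duration of response is worded as time in response, but the only start point given is the first dose, which would add each responder's time to response

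*Combined protocol and SAP*

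**What the plan says.** Section 3.2.2 lists duration of response as a secondary endpoint and describes it, for patients who achieve at least PR, as "how long do they maintain this response before progression". In the Start column of the same table the only entry that can be read is "First dose of JNJ-40346527".

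Other sections bear on the endpoint as follows:

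- **Definitions.** Section 8.2.1 defines overall survival and event-free survival (EFS) only.
- **Populations.** Section 10.1 has no row for duration of response.
- **Methods.** Section 10.2.2 names time-to-event methods for EFS and overall survival only.
- **Progression in responders.** Section 6.3 defines it for a patient with at least PR "who then loses PR based upon the original pre-treatment marrow sample".
- **Marrow schedule.** Section 7.2.5 sets marrows at "Cycle 1 Day 29, Cycle 2 Day 29, Cycle 3 Day 29, and every 3 months following Cycle 3 Day 29", and allows extra ones at the investigator's discretion, for example "at the time of suspected disease progression or disease remission". A footnote in 7.10 puts the later marrows in terms of cycles: "Standard of care bone marrow exams are done at screening and Day 29 for Cycles 1-3, and every 3 months for subsequent cycles".
- **After treatment.** Section 7.7 provides contact every 6 months until death. The 7.10 footnote on follow-up says: "Participants may be contacted by phone, and survival status will be collected and documented".
- **Leaving drug without progression.** Under 6.3, for a patient in CR going to transplant, "JNJ-40346527 should be discontinued 7 days before initiation of the conditioning regimen". Section 4.6 also allows discontinuation for toxicity.

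**The concern.** A response cannot be maintained before it exists, so the row's wording implies a clock that starts when at least PR is first documented. The stated start is earlier. An analyst who follows the Start column reports time to response plus time in response under the name of duration. The error also differs between patients: the slower the response, the longer-lasting it appears. An analyst who follows the wording instead has to choose an origin that the plan does not state, possibly after seeing the data of a handful of responders.

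Duration of response appears twice among the secondary objectives in 2.2 and is one of the efficacy assessments in the synopsis, so it is likely to be reported and compared with other agents.

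A second, weaker question concerns the end of the clock. For a responder who stops drug without progressing, the readable text states neither a scheduled relapse assessment nor a censoring rule for this endpoint. EFS as defined in 8.2.1 needs the same relapse date.

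**Working it through.** **The plan's own figure.** The documents give no number for duration of response. The one design figure that can be reproduced is the per-arm power in 10.3.1 (7 + 7 patients, continue on at least 1 response, promising on at least 3 of 14, 5% against 30%).

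Reject probability = P(X1 ≥ 3) + P(X1 = 2)·P(X2 ≥ 1) + P(X1 = 1)·P(X2 ≥ 2), with X1 and X2 binomial on 7 patients each.

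- At 30%: 0.3529 + 0.3177 × 0.9176 + 0.2471 × 0.6706 = 0.810, against 80% stated.
- At 5%: 0.0274, within the one-sided 5%.

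This depends on the response rate only. Nothing below changes it.

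**Does a shared cell matter?** If the first-dose entry belongs to the duration row, it applies to duration. If it is a merged cell for all four rows, it still covers duration. The End cell for the row is blank as extracted; I give that no weight, since the table may be broken.

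**Do the columns act as clocks?** For the primary endpoint (3.2.1) Start and End frame an observation window for a rate. In 3.2.2, EFS ends 12 months from first dose, which is a time-to-event clock. The columns serve both purposes, so the table does not settle which is meant for duration.

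**What a first-dose clock adds.** Time from first dose = time to first documented response + duration from that response. Cycles are 28 days (6.1) and first dose is Day 1, so with no cycle delay the Day 29 marrows fall:

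- cycle 1: 28 days after first dose
- cycle 2: 2 × 28 = 56 days
- cycle 3: 3 × 28 = 84 days

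Each has a window of ±7 days (7.5). A delay under 6.2.2 would lengthen these. So would a response first seen at a later 3-monthly marrow: patients with stable disease may stay on drug (6.3), and the duration row sets no limit on when the response must occur.

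**Relative size.** Overstatement = time to response ÷ true duration. The true durations below are assumptions.

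| True duration (assumed) | +28 days | +56 days | +84 days |
|---|---|---|---|
| 60 days | 47% | 93% | 140% |
| 90 days | 31% | 62% | 93% |
| 180 days | 16% | 31% | 47% |
| 365 days | 8% | 15% | 23% |

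**Distortion between patients.** Two responders who each stay in response for 90 days, one first documented after cycle 1 and one after cycle 3, would be reported at 28 + 90 = 118 and 84 + 90 = 174 days. The 56-day difference is time to response alone.

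**Number of patients.** At the 30% design rate a full arm has 0.30 × 14 = 4.2 expected responders, so one responder with unclear status is roughly a quarter of the arm's data on this endpoint.

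**The case against.** The best reply is that the row's wording is the actual definition. It speaks of maintaining a response once achieved, and 6.3 says when a responder has progressed. On that reading duration runs from at least PR to loss of PR, and the first-dose entry is a generic start of observation spread over the table. This is a fair reading, and it defeats the inference that the endpoint is firmly fixed at first dose or does not measure how long response lasts. It does not remove the conflict: the only start point printed for the row is the first dose, and no section names another.

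Three further inferences are tempting and are not supported:

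- **That no response can be documented before Cycle 1 Day 29.** Section 7.2.5 allows discretionary marrows, including at suspected remission, and the visit window is ±7 days. The 28, 56 and 84 days hold for the scheduled marrows only.
- **That relapse is not tracked off drug.** Most rows of the schedule in 7.10 are missing from the text available. The follow-up footnote says that survival status is collected, not that nothing else is. Section 7.2.5 allows marrows at suspected progression, 6.3 contemplates relapse after transplant, and EFS requires a relapse date. What can be said is only that no scheduled relapse assessment after stopping drug appears in the readable text.
- **That reported durations would be nearly doubled.** That takes a response first seen after cycle 3 and lost about 3 months later. Over the assumed range above, the overstatement runs from 8% to 140%.

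It is also true that the endpoint is secondary, concerns few patients and does not enter the stage decisions. That limits the importance of the point but does not answer it.

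**Conclusion.** The point holds as a conflict between the endpoint's wording and its only stated start. If the stated start is followed, each response first seen at the scheduled marrows after cycles 1 to 3 is reported about 28, 56 or 84 days (±7) too long, and later responses by more. In relative terms this is 31% to 93% if true duration is 90 days and 16% to 47% if it is 180 days. Both durations are assumptions. The day counts assume 28-day cycles without delay.

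The point about responders who stop drug without progression carries lower confidence, because the schedule rows cannot be read. It is a request for confirmation, not a finding that data are missing.

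The primary endpoint, the 14 patients per arm and the power are unaffected. The change should be made, but the trial's main conclusion does not depend on it.

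**What to change.** 1. In 3.2.2, set the start of duration of response at the date of the first assessment documenting at least PR.
2. Set the end at progression or relapse as 6.3 defines it for responders, and state whether death counts as an event or is censored. Name 6.3 explicitly, because 8.2 carries a separate general definition of progressive disease.
3. Add a duration-of-response row to 8.2.1 with this origin, end and censoring rule, including how transplant, new AML therapy and stopping drug without progression are treated. Name the population in 10.1 and the method in 10.2.2.
4. Report time to response, from first dose to first documented response of at least PR, as a separate quantity.
5. Confirm that dates of relapse, transplant and new AML therapy are recorded at the existing 6-monthly contacts for responders who have stopped drug. If they are not, add them; EFS needs the relapse date as well.

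The cost is protocol wording and, if item 5 is not already covered, a few data items at contacts already planned. No visit, procedure, treatment rule or sample size changes. Compared with a first-dose clock, reported durations will be shorter.
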